- UKU-Side Effect Rating Scale (UKU-SERS): The UKU-SERS [74] is a general rating scale for the registration of unwanted side effects of psychotropic medication. UKU is an acronym for the Danish name "Udvalg for Kliniske Undersøgelser" (Task force for clinical investigations). UKU was a task force of the Scandinavian College of Neuropsychopharmacology (SCNP) working with the development of rating scales and methodological issues in relation to psychopharmacological research. It covers a broad range of different possible side effects and has been widely used in clinical studies since its development and publication in 1987 (e.g. [75,76].
- Epworth Sleepiness Scale (ESS): The ESS is a self-administered questionnaire that provides a measurement of the general level of daytime sleepiness [77]. Since its development, it has been used in several thousand clinical studies (e.g. [78-79]). Sleepiness is a frequent symptom in patients with AN, because starvation results in a fragmentation of sleep and a reduction of slow wave sleep, and thus abnormalities in sleep efficiency and sleep architecture [80,81]. On the one hand, daytime sleepiness is a common side effect of antipsychotics, and specifically olanzapine is known to induce moderate somnolence [82], on the other hand, it has been shown to lead to an improvement of sleep [37] and may thus reduce AN-associated daytime sleepiness.

Table 1 provides a synopsis and schedule of all assessment tools used in OPEN. We have listed many outcome parameters. However, given the multiple comorbidities of AN which were explicitly mentioned in the HTA call 16/97 and the number of potential side effects of olanzapine [55], this multitude of parameters makes sense from a clinical perspective.

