Before asking patients to participate in the trial, the potential adult participant or the potential adolescent participant and their parents or legal representatives will have a discussion with their medical doctor or consultant psychiatrist about the therapeutic effects and potential side effects of the treatment with olanzapine. They will explain the following common and very common side effects for olanzapine according to the BNF: Anticholinergic syndrome; appetite increased; arthralgia; asthenia; eosinophilia; fever; glycosuria; oedema; sexual dysfunction. Psychiatrists will receive training on how to explain these common and very common side effects once trial sites are open to adhere to uniform of clinical explanations with the participants. These side effects are also outlined in the consent form and patient information form in both an electronic and physical copy.

Participants will be informed that the use in this study is off-label. Patients and their families or legal representatives will receive a leaflet about olanzapine and about the study. The leaflet will be approved by the REC and be in compliance with GCP, local regulatory requirements and legal requirements. They will have the opportunity to ask questions.

Page 32 of 60

All members of the research team who will have contact with study participants will have received adult and child safeguarding training.

The capacity assessment during the screening process will be conducted by the clinical teams on site and include an assessment that the potential adult participant or adolescent participant and their parents/legal representatives have the ability to:

- understand the information of the participant information sheet, particularly regarding the effects and potential side effects of olanzapine, the procedures at each study visit and the participant's right to withdraw from the study at any time with no negative implications to their clinical care;
- understand the purpose and nature of the research
- understand what the research involves, its benefits (or lack of benefits), risks and burdens
- understand the alternatives to taking part
- are able to retain the information long enough to make an effective decision.
- Weigh up the options (taking olanzapine or not, taking part in the study or not) and are able to make a free choice

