9.4 Adverse events that do not require reporting

Routine hospitalizations for examinations related to AN standard care will be recorded but do not require reporting.

Additionally, the following known adverse reactions associated with taking olanzapine do not require reporting:

Page 43 of 60

somnolence, weight gain, eosinophilia, elevated prolactin, cholesterol, plasma glucose or HbA1c and triglyceride levels, glucosuria, increased appetite, dizziness, akathisia, parkinsonism, leukopenia, neutropenia, dyskinesia, orthostatic hypotension, anticholinergic effects, transient asymptomatic elevations of hepatic aminotransferases, rash, asthenia, fatigue pyrexia, arthralgia, increased alkaline phosphatase, high gamma glutamyl transferase, high uric acid, high creatine phosphokinase and oedema.

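### The nine-item side-effect list fixed for the consent talk in section 7.2 leaves out effects that the protocol elsewhere calls common or a main concern, and the sections must be reconciled

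*Protocol*

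**What the plan says.** Section 7.2 has the treating doctor discuss therapeutic effects and possible side effects with the patient, and with the parents of adolescents, before the patient is asked to join. It then fixes the content: "They will explain the following common and very common side effects for olanzapine according to the BNF: Anticholinergic syndrome; appetite increased; arthralgia; asthenia". The full list of items is "Anticholinergic syndrome; appetite increased; arthralgia; asthenia; eosinophilia; fever; glycosuria; oedema; sexual dysfunction". Psychiatrists are to be trained so that these effects are explained in the same way at every site. Of the written material it says: "These side effects are also outlined in the consent form and patient information form in both an electronic and physical copy". A leaflet about olanzapine and the study, approved by the ethics committee, is also handed out, and there is time for questions.

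Three other places describe what olanzapine does:

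- Section 3.3.7 says that sleepiness by day is common with antipsychotics and that "specifically olanzapine is known to induce moderate somnolence". It also says that olanzapine may change cholesterol, plasma glucose and blood fats.
- Section 6 names weight gain and its consequences, such as lipid disturbance, as the main concern in adolescents given olanzapine for schizophrenia. It adds that in anorexia nervosa the weight gain is the effect sought.
- Section 9.4 states that "the following known adverse reactions associated with taking olanzapine do not require reporting". Its list opens with "somnolence, weight gain, eosinophilia, elevated prolactin, cholesterol, plasma glucose or HbA1c and triglyceride levels, glucosuria, increased appetite, dizziness, akathisia, parkinsonism, leukopenia, neutropenia" and closes with "rash, asthenia, fatigue pyrexia, arthralgia, increased alkaline phosphatase, high gamma glutamyl transferase, high uric acid, high creatine phosphokinase and oedema".

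**The concern.** Section 7.2 does not give examples. It sets a script, has staff trained to it, and carries it into the forms. If the script is narrower than what the protocol itself says about the drug, a doctor who follows it exactly will not mention effects that the study team already recognises. The participants are 12 to 24 years old, the use is off-label, and for those under 16 a parent consents.

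Two further parts of the plan depend on this content. The capacity assessment in section 7.2 tests whether the person understands the information sheet, in particular its account of effects and side effects. Agreement to take olanzapine is the first item of the primary objective (section 3.1), and the interviews in section 7.9 ask how patients weighed the risks. Both should rest on a risk description that agrees with the rest of the protocol.

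**Working it through.** The protocol gives no count of its own, so the check is a term-by-term comparison of the two lists, followed by a test of the differences against the criterion that 7.2 sets.

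**Inputs.** Section 7.2 lists 9 terms. Section 9.4 lists 28, counting cholesterol, glucose or HbA1c, and triglycerides as three terms, and fatigue and pyrexia as two (the comma between them is missing).

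**Matching.** Pairing synonyms (fever with pyrexia, glycosuria with glucosuria, anticholinergic syndrome with anticholinergic effects), 8 of the 9 terms in 7.2 also stand in 9.4. Sexual dysfunction is the one that does not.

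- In 9.4 but not in 7.2: 28 − 8 = 20.
- If fatigue and pyrexia are read as a single term: 27 − 8 = 19.

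**What the 20 are.**

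- 9 clinical effects: somnolence, weight gain, dizziness, akathisia, parkinsonism, dyskinesia, orthostatic hypotension, rash, fatigue.
- 11 laboratory findings: raised prolactin, cholesterol, glucose or HbA1c, triglycerides, aminotransferases, alkaline phosphatase, gamma glutamyl transferase, uric acid and creatine phosphokinase, together with leukopenia and neutropenia.

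**Test against 7.2's criterion.** Section 7.2 claims to give effects at two frequency levels, common and above, from the BNF. Section 9.4 gives no frequencies. A term's presence in 9.4 therefore does not show that it belongs in 7.2; other text in the protocol has to show that.

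| Effect | What the protocol says elsewhere | In the 7.2 list? |
|---|---|---|
| Sleepiness, somnolence | Common with antipsychotics, and caused by olanzapine (3.3.7); first item in 9.4; measured by a sleepiness scale at all five assessments (3.7) | No |
| Lipid change | Possible olanzapine effect (3.3.7); part of the main concern in adolescents with schizophrenia (6); in 9.4 | No |
| Glucose change | Possible olanzapine effect (3.3.7); in 9.4 | Only glycosuria, which is related |
| Weight gain | Main concern in adolescents with schizophrenia, but the intended effect here (6); second item in 9.4 | Only increased appetite, which is related |
| Dizziness, akathisia, parkinsonism, dyskinesia, orthostatic hypotension | Known reactions (9.4), no frequency given | No |
| Other laboratory findings, rash, fatigue | Known reactions (9.4), no frequency given | No |

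The first row is a contradiction by 7.2's own standard. The next three are effects that the protocol singles out as important and then leaves out of the talk. The last two are open: whether those effects meet the frequency criterion depends on the BNF, which is not part of the documents. A laboratory nature alone does not explain the gaps, because 7.2 itself includes eosinophilia and glycosuria.

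**The case against.** The strongest reply is that the two lists serve different purposes. Section 7.2 is limited by frequency. Section 9.4 is a list of reactions exempt from reporting, whatever their frequency, and much of it is laboratory findings. This stands. A reader might take 20 of 28 as the share of risks withheld from participants. It is not that: it measures how far two lists with different criteria differ. For the same reason, not every 9.4 term has to enter the talk.

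Second, a reader might infer that disclosure as a whole is incomplete, or consent invalid. The documents do not show this. Section 7.2 says that the forms outline these effects, not that they contain nothing else. It also provides a general discussion of side effects and an olanzapine leaflet. The forms and leaflet are not shown and may cover more. What remains is that the nine items are the only side-effect content the protocol fixes for the talk and the training.

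Third, weight gain is the treatment aim in this population and would naturally come up under therapeutic effects. This also largely stands, though it does not cover somnolence or the metabolic changes.

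Fourth, a reader might conclude that the proportion agreeing to take olanzapine is biased upward, or that unannounced effects will depress adherence. Neither is supported. No figure in the protocol links disclosure to uptake, and the premise that participants are not told is unproven. Even the sign is unclear for sedation, since sections 2.1 and 3.3.7 also credit olanzapine with better sleep and possibly less daytime sleepiness. On stopping, section 1.3 reports that personal or study-related reasons for dropout were more common than adverse events.

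Finally, the effects at issue are monitored by UKU-SERS, ESS, laboratory tests and ECG. The fault therefore lies in the wording of disclosure and does not imply undetected harm.

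**Conclusion.** The contradiction is real and the text is wrong as written. On the protocol's own words, sleepiness meets the criterion that 7.2 sets and is missing from it. This assumes that the statement in 3.3.7 about antipsychotics as a class applies to olanzapine, which the same sentence supports. The lipid and glucose changes and weight gain, which the protocol flags itself, appear only through the related items glycosuria and increased appetite. Beyond these, the number of 9.4 reactions that belong in 7.2 cannot be settled without the BNF.

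The point rests on the talk being given as section 7.2 prescribes. It makes no claim about what the unseen forms and leaflet contain, or about any effect on uptake or adherence. It matters because the prescribed talk to young people and their parents would leave out risks that the study team already recognises, and because it is easy to correct.

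**What to change.** Reconcile section 7.2 with sections 3.3.7, 6 and 9.4:

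1. Re-check the 7.2 list against its stated source and state the frequency criterion plainly.
2. Add every reaction that meets the criterion. Somnolence does, on the protocol's own wording.
3. Add the metabolic effects that the protocol flags (lipid and glucose change). Say where weight gain is explained, as a therapeutic effect or as a risk.
4. Check the psychiatrist training, information sheet, consent form and leaflet against that one list and align them. If they already contain more, correct 7.2 and the training to match.

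Isolated laboratory findings in 9.4 that do not meet the criterion need not be added.

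The cost is a wording amendment through the ethics committee, with revised training material and, if the check shows gaps, revised forms. Sample size, assessments and analysis do not change.

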7.3 The randomisation scheme

This is an open-label feasibility trial. Participants will not be randomized. All participants will be treated with olanzapine and will know this.

7.4 Blinding

This is an open-label feasibility trial. Participants will not be blinded. All participants will be treated with olanzapine and will know this.

7.5 Emergency Unblinding

This is an open-label feasibility trial. Participants will not be blinded. Therefore, there is no need to unblind them.

7.6 Baseline data

7.6.1. Screening data

At baseline, we will enter the screening data of those participants who consent to take part in the trial into the database. This screening will take approximately 3 hours. These data include:

Screening Data:

- Inclusion/Exclusion Criteria
- Psychiatric and physical examination
- Laboratory parameter checks to ensure normal ranges throughout the study (Electrolytes and salt/water balance Kidney function, Liver function, Blood count/bone marrow, Plasma glucose (fasting or random) or glycated hemoglobin (HbA1c) and lipid profile- see below values of concern)
- Body temperature
- Electrocardiogram (ECG)
- Screening for Drug or Alcohol Abuse Disorders
- Alcohol, Smoking and Substance Involvement Screening Test (ASSIST)

7.6.2. Standardized assessments:

We will obtain the following baseline data using standardized questionnaires and assessments:

Psychopathology

- Eating Disorder Examination-Questionnaire (EDE-Q)
 - Depression Anxiety Stress Scales (DASS/RCADS)
- Revised Beliefs about Voices Questionnaire (BAVQ-R)
- Self-regulation of Eating Behaviour Questionnaire (SREBQ)
- Yale-Brown Obsessive-Compulsive Scale (Y-BOCS/CY-BOCS)
- Columbia Suicide Severity Rating Scale (C-SSRS)

Rating and Documentation of Side Effects

- Epworth Sleepiness Scale (ESS/ESS-CHAD)
- UKU- Side Effects Rating Scale (UKU-SERS)

Health Economy and Quality of Life

- EQ-5D-YTM
- Child, Adolescent and Adult Service Use Schedule (CAA-SUS)
- Eating Disorders Symptom Impact Scale (EDSIS)

Laboratory Parameters (values of concern) [47]

- o Electrolytes and salt/water balance
 - K+ <3.5--<3.0 2
 - Na+ <135--<130 3
 - Mg++ 0.5-0.7--<0.5 4
 - PO4-- 0.5-0.8-- <0.5 5
- Kidney function
 - o Urea >7-- >10

Page 34 of 60

- \circ Liver function
 - o Bilirubin >20-->40
 - AlkPase >110-->200
 - AsT >40-- >80
 - ALT >45-->90
 - GGT >45-->90
- o Blood count/bone marrow
 - WCC <4.0-<2.0
 - Neutrophil count <1.5-<1.0
 - Hb <11-<9.0
 - Acute Hb drop (MCV and MCH raised no acute risk)
 - Platelets <130- <110
- Plasma glucose or HbA1c and lipid profile [96]
 - o Total cholesterol 5mmol/L or less
 - o LDL cholesterol 3mmol/L or less
 - Triglycerides <1.7mmol/L

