3.5 Secondary endpoints/outcomes

The secondary objective is feasibility (completeness and summary statistics) of recording the following measures at baseline:

Demographics and the Alcohol, Smoking and Substance Involvement Screening Test (ASSIST)

Page 25 of 60

And of the following measures at baseline (where applicable), 8 weeks, 16 weeks, 6 months, and 12 months post-baseline:

Height, weight, BMI, ED psychopathology questionnaires- (RCADS, EDE-Q, BAVQ-R, SREBQ), General psychopathology assessments and questionnaires-(DASS, RCDADS, Y-BOCS, C-SSRS), Health economic and quality of life assessments (EQ-5D-Y, CAA-SUS, , EDSIS,) olanzapine plasma levels (8 weeks only), Physical examination measures, ECG, laboratory parameters, ESS, ESS-CHAD and quality of adverse events reporting (UKU-SERS).

Also to assess willingness to participate in an RCT (blinded, placebo-controlled).

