3.6.3 Change in measures over time

Change in the measures as listed in section 3.5 will be explored/described to inform a future definitive study design.

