3.7 Schedule of events

Synopsis and schedule of OPEN outcomes/assessment tools in the feasibility study. The superscript numbers indicate, who will perform the scheduled assessments: ¹Resercher, ²The study participant's clinical treatment team, ³Qualitative Researcher. * if procedure is performed on the day of the Screening visit, it does not need to be repeated; items highlighted in green are standard care procedure.

Methods/Assessments	Screening	Baseline	Igniighted in Assessment at			Assessment at
		Assessment (≤ 7-10 days following Screening)	8 weeks (±7 days)	16 weeks (±7 days)	6 months (±7 days)	12 months (±7 days)
Informed Consent	X1	ocreening)				
Clinical Examinations						
- Inclusion/Exclusion Criteria	X1					
 Psychiatric and physical examination 	X ^{1,2}		X1.2	X ^{1,2}	X ^{1,2}	X ^{1,2}
 Weight, height, blood pressure (BP), body temperature 	X ^{1,2}	X ^{1,2*}	X ^{1,2}	X ^{1,2}	X ^{1,2}	X ^{1,2}
- Laboratory parameters (Electrolytes and salt/water balance - Kidney function, Liver	X ^{1,2}		X1.2	X ^{1,2}	X ^{1,2}	X ^{1,2}
function Blood count/bone marrow, Fasting glucose and lipid profile)						
- Electrocardiogram (ECG)	X ^{1,2}		X1.2	X ^{1,2}	X1.2	X1.2
- Concomitant Medications	X1	X1*	X1	X1	X1	X1
- Serum Pregnancy Test	X1,2		X1,2	X ^{1,2}	X1,2	X1.2
IMP dispensing		X1.2	X1.2	X ^{1,2}	X1.2	
Screening for Drug or Alcohol Abuse Disorders						
 Alcohol, Smoking and Substance Involvement Screening Test (ASSIST) 		X1				
Treatment as Usual						
 Treatment elements checklist 		X1	X1	X1	X1	X1
Adherence measures						
- Olanzapine plasma level			X ^{1,2}			
- Pill count			X1.2	X ^{1,2}	X ^{1,2}	X ^{1,2}
AE recording/reporting			X1	X1	X1	X1
 UKU Side Effects Rating Scale 			X1	X ¹	X1	X ¹
Eating Disorders Psychopathology						
 Eating Disorder Examination-Questionnaire (EDE-Q) 		X1	X1	X1	X1	X1
 Revised Beliefs about Voices Questionnaire (BAVQ-R) 		X1	X1	X1	X1	X ¹
 Self-regulation of Eating Behaviour Questionnaire (SREBQ) 		X1	X1	X1	X1	X ¹
General Psychopathology						
- Depression Anxiety Stress Scales (DASS/RCADS)		X1	X1	X1	X1	X1
- Yale-Brown Obsessive-Compulsive Scale (Y-BOCS/CY-BOCS)		Х	Х	X1	X1	X1
- Columbia Suicide Severity Rating Scale (C-SSRS)		X1	X1	X1	X1	X1
Rating and Documentation of Side Effects						
- Epworth Sleepiness Scale (ESS/ESS-CHAD)		X1	X1	X1	X1	X1
Health Economy and Quality of Life						
- EQ-5D-Y™		X1			X1	X1
 Child, Adolescent and Adult Service Use Schedule (CAA-SUS) 		X1			X1	X1

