10.3.3 Secondary outcome analysis

Descriptives (including completeness) will be reported for the following measures: demographics, alcohol, smoking and substance use, body weight and BMI, ED psychopathology, general psychopathology, health economic and quality of life assessments, laboratory parameters (kidney function, liver function, blood count, plasma glucose, HbA1c and lipid profile), drug adherence and safety.

The safety outcomes will include:

- Summary statistics on "concerning" and "alerting" laboratory and ECG parameters according to [47]
- Descriptives of other safety parameters
- Summary of reported AEs and SAEs

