15. APPENDICES

Amendment History

Amendment No.	Protocol version no.	Date issued	Author(s) of changes	Details of changes made
1	1.1	04/03/2022	[name]	Detailed section on distress management, safeguarding and confidentiality management has been added as per REC recommendation, clarifications have been made to the inclusion and exclusion criteria to avoid confusion and improve consistency with the EDC.
2	1.2	11/08/2022	[name]	Minor clarifications on measures used including explaining use of the EQ-5D- Y questionnaire, CAA-SUS, as well as correcting an erroneous deletion of UKU-SERS from the Schedule of Events. A clarification that carers will have an opportunity to voice their opinion at the Week 16 qualitative interview.
3	1.3	02/12/2022	[name]	Minor clarifications of acceptable assessments of plasma glucose – both fasting plasma glucose and random plasma glucose are acceptable as well as glycated hemoglobin measurement.

List details of all protocol amendments here whenever a new version of the protocol is produced.

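### Section 7.6.2 requires UKU-SERS at baseline but the schedule does not mark it, and the lipid values of concern run in the opposite direction to the other laboratory limits

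*Protocol*

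**What the plan says.** **UKU-SERS.** Section 7.6.2 opens with "We will obtain the following baseline data using standardized questionnaires and assessments" and, under side effects, lists "UKU- Side Effects Rating Scale (UKU-SERS)" next to the Epworth scale. In the schedule of events (3.7), the row "UKU Side Effects Rating Scale" is empty at Screening and at Baseline and marked at the four follow-up visits. Section 3.5 names UKU-SERS in a list introduced by "And of the following measures at baseline (where applicable), 8 weeks, 16 weeks, 6 months, and 12 months post-baseline". Section 3.6.3 adds: "Change in the measures as listed in section 3.5 will be explored/described to inform a future definitive study design". Section 10.3.4 likewise plans exploratory change over time in the 10.3.3 measures, which include safety.

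**Lipids.** Section 7.6.2 also contains a list of laboratory values of concern, attributed to reference [47]. Its lipid part, attributed to [96], begins "Total cholesterol 5mmol/L or less" and continues with LDL at or below 3 mmol/L and triglycerides below 1.7 mmol/L. Section 7.6.1 points to this list for laboratory checks, including the lipid profile. Section 10.3.3 plans to summarise concerning and alerting "laboratory and ECG parameters according to [47]".

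**The concern.** The trial has no comparator (section 4), so on any side-effect scale the patient's own rating before olanzapine is the natural reference. Several symptoms of interest can come from the illness or from the drug. Section 3.3.7 says this of sleepiness, and adds that olanzapine may also improve sleep. Without a pre-drug UKU rating, a symptom recorded at 8 weeks could be old, new, worse or better, and the scale could not tell which. A pre-dose rating cannot be obtained later, and section 10.7 rules out imputation. UKU-SERS carries extra weight because section 9.4 exempts several known reactions from reporting, among them somnolence, dizziness, akathisia and anticholinergic effects.

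Lipid disturbance is a metabolic harm that sections 3.3.7 and 6 both mention. A limit written in the wrong direction would, if used, count unraised results as concerning and pass raised ones.

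**Working it through.** The protocol states no figure on this point, so the check is mainly a comparison of passages.

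**Step 1: is the UKU conflict real and current?**
- Section 7.6.2: UKU-SERS is to be obtained at baseline.
- Section 3.7: no mark at Screening or Baseline; marks at 8 weeks, 16 weeks, 6 months and 12 months.
- Lost table cells are an unlikely explanation: the EDE-Q, DASS/RCADS and ESS rows of the same table all carry a baseline mark.
- Section 3.5 limits baseline collection to measures for which it is applicable, which fits either reading.
- The amendment history records "correcting an erroneous deletion of UKU-SERS from the Schedule of Events" at version 1.2. This is background only. The row in the current version 1.3 is the one that still lacks a baseline mark.
- Section 7.7 presents 3.7 as the overview of all assessments and their timing. A site could reasonably work from it, but nothing says that it overrides 7.6.2.

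**Step 2: what would the missing rating do to a symptom count?** The documents give no UKU item prevalences, so these inputs are assumptions:
- *b*: share with the symptom before treatment, 10% to 50%, all persisting
- *i*: share of the remaining patients who develop it, 10% to 20%
- *n*: 55 patients, all rated

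Formulas: patients showing the symptom = n × [b + (1 − b)i]; newly affected = n × (1 − b)i; pre-existing share = b / [b + (1 − b)i].

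| b | i | Showing symptom | Newly affected | Pre-existing share |
|---|---|---|---|---|
| 10% | 10% | 55 × 0.19 = 10.45 | 55 × 0.09 = 4.95 | 0.10/0.19 = 53% |
| 10% | 20% | 55 × 0.28 = 15.4 | 55 × 0.18 = 9.9 | 0.10/0.28 = 36% |
| 50% | 10% | 55 × 0.55 = 30.25 | 55 × 0.05 = 2.75 | 0.50/0.55 = 91% |
| 50% | 20% | 55 × 0.60 = 33.0 | 55 × 0.10 = 5.5 | 0.50/0.60 = 83% |

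So 36% to 91% of the patients counted would have had the symptom already. Symptoms that resolve on treatment would lower this share, and their improvement would also go unseen without a baseline.

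**Step 3: direction of the laboratory limits in 7.6.2.**
- Electrolytes: low values listed (for example potassium below 3.5, sodium below 135).
- Kidney and liver: high values listed (for example urea above 7, ALT above 45).
- Blood count: low values listed (for example white cells below 4.0, platelets below 130).
- Lipids: total cholesterol ≤5, LDL ≤3, triglycerides <1.7 mmol/L. Low values are listed, whereas section 9.4 names elevated cholesterol and triglycerides as the known reaction.

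The first three groups give the abnormal side; the lipid lines give the acceptable side. Read literally, a total cholesterol of 4 mmol/L is of concern and one of 7 mmol/L is not.

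**Step 4: does the lipid error reach the analysis?** Section 7.6.1 refers to this list for the laboratory checks, so it has an operational use. Section 10.3.3 classifies according to [47], while the lipid lines cite [96] and give one limit each instead of the paired tiers used for most other parameters. The link to the summary is therefore possible but not stated. In the reference list, 96 is a paper on pilot-study sample size and the cholesterol web page is 97.

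**The case against.** A reader might infer that the study will lack a UKU baseline and will mislabel side effects. The documents do not support that. Section 7.6.2 does require the rating, and no text says which section sites follow. The loss is conditional on the schedule being followed.

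A reader might also infer that no pre-drug reference would remain. That goes too far. The ESS covers sleepiness and is marked at baseline, as are the DASS/RCADS, Y-BOCS/CY-BOCS, C-SSRS and EDE-Q. Screening includes a psychiatric and medical history, physical examination, laboratory tests and ECG. What would be lost is the item-level comparison on UKU-SERS.

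On lipids, the tempting reading is that the safety summary will be inverted. That is not established, for the reason in step 4. Section 10.3.3 also plans plain descriptives of the lipid profile, which need no cut-off, and section 9.4 makes the intended direction clear to an attentive reader.

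Nor can a fixed inflation factor be claimed, since any such figure only restates the prevalences assumed.

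Finally, section 2.4 says that the study is not meant to verify safety, and change over time is exploratory. This lowers the stakes. It does not remove them, because section 3.2 makes the collection of drug-safety data a feasibility objective meant to inform an RCT.

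All these limits on the consequence stand. The two textual defects are untouched by them.

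**Conclusion.** The point holds in conditional form. Sections 7.6.2 and 3.7 contradict each other on baseline UKU-SERS. If the schedule is followed, the planned change from baseline cannot be computed for that scale, and new or worsened symptoms cannot be separated from old ones. The 36% to 91% range shows how large the ambiguity could be under the assumptions listed; it is not an estimate for this trial. The lipid lines run opposite to their heading and to section 9.4, and any check programmed or applied literally would work backwards. Their effect on the 10.3.3 summary is uncertain. Neither defect touches the recruitment, adherence or completion endpoints. Both should be corrected, since the repair is nearly free and a missed pre-dose rating cannot be recovered.

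**What to change.** 1. Reconcile 3.5, 3.7 and 7.6.2 by marking UKU-SERS at Baseline in 3.7, to be completed before the first dose. The schedule dispenses the drug at that same visit, so the order should be stated.
2. Report UKU-SERS as change from baseline and as items new or worsened since baseline. If some participants have no pre-dose rating, state how many and leave them out of those two summaries.
3. Have the sponsor restate the three lipid lines in the same direction as the other values of concern and confirm the cut-offs. This review proposes none, because section 10.8 ties blood results to continuing olanzapine.
4. State whether the lipid lines feed the concerning/alerting summary in 10.3.3, and correct the citation from [96] to the cholesterol page, which is 97 in the list.

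The cost is one rating that 7.6.2 already requires, at an existing visit, and a few lines of text.
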